Comparative Effectiveness of School and Community-Based Caries Prevention Programs for Children in Underserved, Low Income, Hispanic Communities

This is a pragmatic, cluster, randomized controlled, non-inferiority trial which compares simple vs complex caries prevention. The study is being conducted in schools, at community-based locations, or at the New York University College of Dentistry. Simple is defined as fluoride varnish + silver diamine fluoride. Complex is defined as fluoride varnish + traditional sealants + interim therapeutic restorations (also referred to as temporary fillings). All interventions are: currently used in clinical practice; have American Dental Association billing codes; and, depending on the state and third party administrator, are compensated by Medicaid.

Principal Investigator:	[name] Department of Epidemiology & Health Promotion [name] [contact] [contact]			
Funding Support:	Patient Centered Outcomes Research Institute [name] [contact] [contact]			
Study Intervention:	[contact] [contact] The trial compares two caries prevention protocols delivered 1 time or 2 times each year in elementary schools, at community-based locations, or at the New York University College of Dentistry: a novel simple intervention of fluoride varnish + silver diamine fluoride vs the traditional complex intervention of fluoride varnish + traditional sealants + interim therapeutic restorations. 30 elementary schools will be randomized to receive simple prevention twice per year and 30 elementary schools will be randomized to receive complex prevention twice per year. The remaining 16 schools will receive simple prevention			
IRB Number:	S17-00578			

Initial version: V2 MAY 25, 2017

	$1 \vee 2 \vee 1 \vee 1 \wedge 1 \vee 2 \vee 2 \vee 1 \vee 1 \wedge 1 \vee 2 \vee 2 \vee 1 \vee 1 \wedge 1 \vee 2 \vee 2 \vee 1 \vee 1 \vee 1 \vee 2 \vee 2 \vee 1 \vee 1 \vee$
Amended:	V3 July 27, 2018
Amended:	V4 September 6, 2018
Amended:	V5 January 14, 2019
Amended:	V6 February 27, 2019
Amended:	V7 August 13, 2019
Amended:	V8 August 22, 2019
Amended:	V9 September 12, 2019
Amended:	V10 February 13, 2020
Amended:	V11 October 19, 2020
Amended:	V12 January 6, 2021
Amended:	V13 April 13, 2021
Amended:	V14 June 16, 2021
Amended:	V15 December 15, 2021
Amended:	V16 January 26, 2022
Amended:	V17 April 1, 2022
Amended:	V18 July 27, 2022

Table of Contents

S	TUDY S	SUMMARY	6

Title	Comparative Effectiveness of School and Community-Based Caries Prevention Programs for Children in Underserved, Low Income, Hispanic Communities
Short Title	CARIEDAWAYNYC
IRB Number	S17-00578
Study Type	Human
Study Design	Pragmatic, cluster, randomized controlled, non-inferiority trial
Study Intervention	Simple prevention (fluoride varnish + silver diamine fluoride) vs complex prevention (fluoride varnish + traditional sealants + interim therapeutic restorations)
Study Duration	5 years
Study Location(s)	The study will be conducted in New York City Title 1 Elementary Schools, community-based locations, or at the New York University College of Dentistry
Primary Objective	To determine if the newer simple caries prevention is not inferior to the traditional complex caries prevention
Sample Size	76 schools (approximately 20,000 children)
Diagnosis and Main Inclusion Criteria	The disease/condition is untreated caries. All children in the participating schools with informed consent will be included. The only exclusion criteria are children not in the participating schools, children without informed consent and children that are allergic to silver.
Study Product and Planned Use	Silver diamine fluoride (Advantage Silver Arrest). The liquid is administered topically to carious lesions, as well as pits and fissures of posterior teeth.
Control / Comparison	The new simple prevention will be compared to the traditional complex prevention.
Statistical Methodology	Primary outcomes include caries arrest, caries prevention, and quality of life. We will assess these using multilevel binomial regression and generalized estimating equations.

1 Introduction

This study will be conducted in compliance with the protocol approved by the Institutional Review Board (IRB), Good Clinical Practice (GCP) guidelines, and applicable New York University Medical Center (NYUMC) and federal regulatory requirements.

1.1.2 Education

Oral health has larger connections to general health and child development, such as academic performance and quality of life. Oral health also affects children's education. Children with untreated caries and associated toothaches have more school absences, cannot pay attention in school, do not keep up with their peers academically, and have lower standardized test scores4^{-8.} Additionally, children who require dental care in a traditional dental office frequently miss school.

1.1.3 Need

Based on 3 years of conversations, surveys, and guidance, parents and stakeholder partners in New York City requested school-based caries prevention⁹⁻¹⁰, and tracking the following patient-centered outcomes: untreated cavities, quality of life, and school performance. Further, these parent and stakeholder partners participated in planning, designing, and piloting the proposed study. These partners are also participating in the proposed study's conduct, dissemination, and implementation.

1.1.4 Geography

NYC elementary schools serve over one million children of varying socioeconomic and racial/ethnic backgrounds, many of which are from those demographic groups with the highest oral health needs. This initiative focuses on improving the oral health of NYC children. We will enroll 76 schools across NYC to receive alternative caries prevention treatments.

1.2 Study Aims

The overall goal of this study is to measurably improve oral health equity. Towards this goal, we will compare "simple" and "complex" prevention, two packages of interventions designed to prevent and arrest dental caries. The study design is a cluster randomized non-inferiority pragmatic trial. Both preventive interventions are expected to be equally effective in improving health equity. The major difference in the two protocols is that "simple" prevention costs

approximately 25% of "complex" prevention. Simple also takes approximately 25% of the time of complex prevention. Therefore, if simple and complex are found to be equally effective, for the same time and cost, simple prevention could improve health and health equity to approximately 3 times the number of children as complex prevention.

Our prior work, and data from systematic reviews, indicates that the protocols we propose should be similarly effective in both arresting current caries and preventing subsequent caries by 50% to 80%. Thus all children should benefit from the proposed preventions. We will collect data on oral health and child quality of life, and assess student academic performance.

The study consists of three groups: (1) a group receiving simple prevention twice per year; (2) a group receiving complex prevention twice per year; and (3) a group receiving simple prevention once per year.

We will select 76 elementary schools to participate in the program over a five-year period. 30 elementary schools will be randomized to receive simple prevention twice per year and 30 elementary schools will be randomized to receive complex prevention twice per year. The remaining 16 schools will receive simple prevention once per year. The care will be provided in schools, community-based locations or at the New York University College of Dentistry.

The inclusion criteria for the schools enrolled in groups (1) and (2) include: A Hispanic/Latino population of at least 50% and a free and reduced lunch population of at least 80%. The remaining racial/ethnic and socioeconomic distribution of these schools will include children from any race/ethnicity and economic background. The inclusion criteria for schools in group (3) include any elementary school in New York City and will be selected to include representation from every major racial/ethnic group and socioeconomic level.

For the purposes of the analysis on dental-related service use and costs among Medicaid beneficiaries, all children participating in Medicaid of elementary school age will be included in the analysis, except for children in participating schools that do not provide informed consent to provide oral health and Medicaid dental service use data.

The Primary Specific Aims are to:

- 1. Determine the non-inferiority of simple vs complex caries prevention for preventing new caries (primary prevention).
- 2. Determine the non-inferiority of simple vs complex caries prevention for arresting current caries (secondary prevention).
- 3. Determine the impact of simple vs complex prevention on child oral healthrelated quality of life
- 4. Determine the impact of once per year vs twice per year care on the arrest and prevention of caries

Notably, toothaches or office based dental care reduces in-class learning time. If the caries prevention programs are as effective as predicted, knowing the time/trade-off will be important. Thus a secondary outcome of the study will be school performance (school absence and student achievement). To insure accurate assessments, program participants will be compared to children in their own schools and to children in NYC "peer schools" not participating in the study. No additional data is collected for educational outcomes from participants.

The Secondary Specific Aims are to:

- 1. Determine the impact of prevention vs no prevention on school absence
- 2. Determine the impact of prevention vs no prevention on standardized test performance
- 3. Determine the impact of simple vs complex prevention on school absence and test performance

The exclusion criteria will be those: (1) not attending participating schools, (2) those attending participating schools without informed consent, or (3) those attending participating schools with informed consent, but without assent and (4) those allergic to silver.

For the purposes of the analysis on dental-related service use and costs among Medicaid beneficiaries, the only excluded groups are (1) children not participating in Medicaid will be excluded and (2) children participating in Medicaid in Caried*Away* schools, but without informed consent to provide oral health and Medicaid dental service use data.

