2.2 Secondary Objective(s)

To compare the effectiveness of simple prevention when provided twice yearly versus once yearly.

To determine if children receiving either simple prevention or complex prevention will have reduced school absence and higher academic performance when compared to matched students in non-participating schools.

To determine if children receiving simple prevention or complex prevention will have reduced dental service use and costs in Medicaid when compared to matched students in non-participating schools.

3 Study Design

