7.2 Statistical Methods

For caries arrest, we will first determine the per-patient proportion of carious lesions treated with simple versus complex prevention that stayed arrested throughout the length of the study. The percentage of arrested caries (at the child level) will be modeled using multilevel binomial regression. Our noninferiority margin, δ , is set at 10%. Our null hypothesis is that simple prevention is not inferior to the complex prevention by at least δ : π_{simple} - $\pi_{\text{complex}} \ge \delta$. Our alternative hypothesis is that π_{simple} - $\pi_{\text{complex}} < \delta$. We will use differences in effect sizes as estimated by confidence intervals to determine clinical non-inferiority of the two prevention methods. For the prevention of new caries, we will use generalized estimating equations (GEE) with a logit link (caries prevalence) and a negative binomial link (caries incidence), assuming an exchangeable correlation matrix, to evaluate longitudinal effects of comprehensive care untreated decay. We will identify the number of teeth at risk for each child during each follow-up interval and determine the number of those teeth in which new caries is observed at the examination that ends that interval. Primary teeth lost in each interval and new permanent teeth will not contribute to data for that interval. To explore non-linear trends in untreated decay between simple and complex prevention, we will use generalized additive models (GAMs) with non-parametric smoothers. Longitudinal effects of simple and complex prevention on academic outcomes, compared to untreated children, will be analyzed using propensity score-matching and multilevel modeling. First, we will estimate propensity scores for each participant at baseline, establishing the probability of treatment assignment conditional on observed covariates (e.g., prior academic performance). Propensity scores will be used to match treatment students to students not receiving treatment, considering multiple forms of matching
such as nearest neighbor and caliper. Treated students and matched comparators will then be analyzed using multilevel mixed effects linear regression (for academic achievement) and Poisson regression (for school absences).

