- b. In-Class or Zoom Oral Health Education (OHE) Presentations at least once per semester: NYUCD Caried*Away* staff will provide in-class or Zoom OHE to each class at each school once per semester. This allows NYUCD Caried*Away* staff to engage with all teachers/staff as well as each student. Additional personalized pre-populated principal recruitment letters, the parent/guardian alternate location recruitment letter, the NYU Langone Health COVID-19 research participation information sheet and blank informed consent forms may be provided at this time.
- c. Informational tabling at least once per semester: NYUCD Caried*Away* staff will provide parent/guardian informational tabling during student arrival and students dismissal time. This allows parents to meet NYUCD Caried*Away* staff, learn about the program, review and receive the personalized pre-populated principal recruitment letter, explain billing procedures, receive the informed consent form, and ask any questions they may have.
- d. Completed signed and dated informed consent forms are returned to the designated school staff to be kept and checked for completeness. NYUCD Caried*Away* staff will collect these consents 2 weeks prior to a scheduled treatment week and ensure an additional check for completeness.

The parent or guardian will sign the completed paper or electronic informed consent document prior to any study-related assessments or procedures. Consent may be withdrawn at any time throughout the course of the study.

A separate picture of page 1 and page 2 of the completed, signed and dated paper informed consent is taken with the iPad camera and each image is saved and stored in the electronic dental record for each child in the manage subject page within the child's electronic dental record on the Apple iPad.

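### The academic aims have no agreed untreated comparator (same schools, other schools, or any untreated child), and the randomised simple versus complex academic comparison has no analysis of its own

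*Combined protocol and SAP*

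**What the plan says.** Three sections of the combined protocol and SAP describe the untreated comparator for the academic outcomes.

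- Section 1.2 uses two groups without ranking them: "program participants will be compared to children in their own schools and to children in NYC 'peer schools' not participating in the study".
- Section 2.2 names one. Treated children are expected to show "reduced school absence and higher academic performance when compared to matched students in non-participating schools".
- Section 7.2 does not say which schools the untreated children come from: "Longitudinal effects of simple and complex prevention on academic outcomes, compared to untreated children, will be analyzed using propensity score-matching and multilevel modeling". Propensity scores will then "match treatment students to students not receiving treatment, considering multiple forms of matching".

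The propensity model is described as "establishing the probability of treatment assignment conditional on observed covariates (e.g., prior academic performance"), so it adjusts for measured characteristics only.

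Section 8.24 adds that, in participating schools, programme staff "will provide in-class or Zoom OHE to each class at each school once per semester". The same section makes these events subject to each school's memorandum of understanding and to ad hoc change because of COVID-19.

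Section 1.2 lists three secondary aims. Aims 1 and 2 compare prevention with no prevention, on absence and on test performance. Aim 3 compares simple with complex prevention on both outcomes. By sections 3.1 and 6.5.1, 60 schools are randomised between twice-yearly simple and twice-yearly complex prevention, while 16 further schools are selected, not randomised, for once-yearly simple prevention.

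**The concern.** Aims 1 and 2 ask what prevention does compared with no prevention. The answer depends on who stands for no prevention, and the analysis section leaves this open between two groups that differ in ways bearing on absence and test scores.

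A child in a participating school is untreated mainly because no consent or assent was given. Families who return a consent form may differ from those who do not in ways that also affect attendance and achievement. Matching on measured covariates can reduce that difference but cannot be relied on to remove it. The same children are also meant to receive the classroom education, so they are not a group without the programme.

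Aim 3 raises a different problem. It is the one academic question that randomisation can answer, but no direct simple versus complex analysis is written down. If the simple group in the academic analysis includes the 16 selected schools, the comparison mixes treatment type with visit frequency and with a different kind of school.

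**Working it through.** The plan gives no sample size, power, effect size or error rate for the academic outcomes; section 7.1 is powered on caries arrest and prevention only. There is no figure to reproduce, so the check is mainly a reading of the sections, with some arithmetic on size.

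**1. Comparator for Aims 1 and 2**

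| Section | Same-school untreated children | Non-participating schools |
|---|---|---|
| 1.2 Study Aims | yes | yes |
| 2.2 Secondary Objective(s) | not named | yes |
| 7.2 Statistical Methods | allowed | allowed |

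Section 7.2 neither ranks the two nor says what follows if they differ. Its Medicaid analysis does settle the matter: the comparators there are children in non-participating schools, with adjustment for selection into a participating school. Section 1.2 also removes participating-school children without consent from that analysis.

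**2. Who the same-school comparators are**

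Section 1.2 excludes children in participating schools who lack consent, who have consent but not assent, or who are allergic to silver. The first group should be much the largest. Section 6.1.1 lets newly enrolled students join each year.

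For scale, section 6.6 uses 35% as a national starting value for the consent rate, and section 7.1 expects 235 participants per school. If 35% applied here, which is an assumption:

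- children per school = 235 / 0.35 = 671
- non-participants = 671 − 235 = about 436 for every 235 enrolled.

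The same-school pool would be large enough for the choice of comparator to matter.

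**3. What the same-school contrast estimates**

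Let D be the true effect against no programme, s the share of D that same-school comparators also obtain through the classroom education, and b the selection bias left after matching. Then

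same-school contrast = (1 − s) × D + b.

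Neither s nor b is given in the documents. With b = 0:

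- s = 0 gives D
- s = 0.25 gives 0.75D
- s = 0.50 gives 0.50D.

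Suppose, as an illustration, that a two-sided 5% test of D has 80% power, so its expected z is 1.96 + 0.84 = 2.80, and that the same-school test has the same standard error. Power is then Φ(0.75 × 2.80 − 1.96) = 56% at s = 0.25, and Φ(0.50 × 2.80 − 1.96) = 29% at s = 0.50. A same-school comparison may well be more precise than this assumes, so the loss of power could be smaller. The shift in what is estimated would remain.

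Education alone shrinks the effect for any s below 1 but does not reverse it. A changed sign needs b < −(1 − s) × D, that is, adverse residual selection larger than the diluted effect.

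**4. Aim 3 and the 16 selected schools**

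Assuming equal cluster sizes, as section 7.1 does:

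- randomised simple: 30 × 235 = 7,050
- selected once-yearly simple: 16 × 235 = 3,760 (the figure in 7.1)
- all simple: 7,050 + 3,760 = 10,810
- non-randomised share: 3,760 / 10,810 = 34.8%.

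These 16 schools also differ by design. Randomised schools must be at least 50% Hispanic/Latino and at least 80% eligible for free or reduced lunch; the selected schools may be any New York City elementary school (sections 1.2 and 3.1).

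**The case against.** The strongest reply is that section 2.2 already names the comparator. That is right as far as it goes. A reader might infer that nothing in the plan decides the matter, and the documents do not support that. The supportable point is that 1.2 and 7.2 do not follow 2.2.

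The same-school contrast also has a real merit. It holds the school constant, whereas participating schools come from those that showed interest (section 3.1), so a between-school contrast carries its own selection. This is why the same-school comparison should be kept as supportive.

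Three further inferences are tempting and should not be drawn:

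- That the same-school children are families who refused. The group also includes unreturned forms, children without assent and children allergic to silver. The classroom education is planned, not guaranteed.
- That the two contrasts will point in opposite directions. Education alone only dilutes; a reversal needs adverse selection of a size the documents give no reason to assume.
- That the false-positive rate is inflated. This requires a rule that success on either contrast suffices. The plan has no such rule, and the two groups in 1.2 can be read as corroborating each other.

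On Aim 3, section 7.3 promises analysis of participants as randomised, and the multilevel model in 7.2 could carry a simple versus complex term. So it would be wrong to say that the plan discards the randomisation, or that it states the 16 schools will be pooled. But the direct contrast is not written out, and an as-randomised rule cannot place schools that were never randomised.

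Leaving several matching methods under consideration is missing detail rather than an error.

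**Conclusion.** The concern holds in two limited parts. First, the comparator for secondary Aims 1 and 2 is inconsistent across 1.2, 2.2 and 7.2, and one permitted choice, same-school untreated children, does not estimate prevention versus no prevention cleanly. This rests on the exclusion criteria and on the planned classroom education. The size of any dilution or selection bias cannot be obtained from the documents; the 0.75D and 0.50D values and the power figures are illustrations under assumed s, no residual bias, 80% starting power and equal standard errors.

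Second, Aim 3 lacks a stated direct analysis in the randomised schools. Planned enrolment puts about 35% of simple-prevention participants in non-randomised, once-yearly schools, assuming 235 per school.

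Both parts concern secondary outcomes and leave the primary caries conclusions untouched. They should be corrected because the academic claims would otherwise rest on an unsettled comparison.

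**What to change.** In sections 1.2 and 7.2:

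1. Name matched students in non-participating schools as the main comparator for secondary Aims 1 and 2, consistent with 2.2. Include school as a level in the model and adjust for selection into participating schools, as the Medicaid analysis already proposes.
2. Keep the same-school contrast as supportive. State alongside it that comparators are mainly children without consent or assent and that they may have received the classroom education.
3. Analyse Aim 3 directly as twice-yearly simple versus twice-yearly complex in the 60 randomised schools, by assigned arm, allowing for school clustering and without matching to untreated children. Leave the 16 once-yearly schools out of this contrast.

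The cost is wording; no new data collection is required. The main contrast for Aims 1 and 2 will probably have wider intervals than a same-school comparison, and adjustment for school selection may be incomplete.
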